# Relationship Between Acute Phase Markers and Post-operative Pain in Laparoscopic Cholecystectomy: An Observational Study

March 3, 2023

**Background:** Many patients undergoing laparoscopic cholecystectomy are prone to developing acute and chronic post-operative pain.

The aim of the study is to show a possible correlation between pain and acute phase proteins in order to:

- predict the severity of pain;
- select most suitable pain relief therapy for the patient.

**Materials and methods:** The day after surgery, some serum markers are determined by a blood sample. The markers analyzed are:

- Leukocytes;
- C-reactive protein (CRP);
- D-dimer;
- Fibrinogen;
- Neutrophil-to-Lymphocyte Ratio (NLR).

Pain level is assessed using the NRS scale at different times:

- 1st post-operative day;
- 7th post-operative day;
- One month after surgery;
- Three months after surgery;
- Six months after surgery.

Other data collected for the study are: gender, age and BMI.

**SAP:** Statistical Analysis Plan was expressed as percentages, median, and range of values. Differences between continuous variables were analyzed with the Mann-Whitney U test, whereas differences between categorical variables were evaluated with the chi-square or the Fisher's exact test, when appropriate. Variables achieving statistical significance ( $P<0.05$ ) at univariate analysis were entered in a backward multivariate logistic regression model, removing the variable if  $P$  more than 0.10.  $P$  less than 0.05 was considered statistically significant. Statistical analysis was carried out with the SPSS software packaging (SPSS Inc., Chicago, IL), version 13.

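### The study can support prediction of pain but cannot by itself show which analgesic therapy suits whom, and surgical indication, a possible common cause of marker level and pain, is not among the listed data

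*Combined protocol and SAP*

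**What the plan says.** The Background gives the aim in one sentence: "The aim of the study is to show a possible correlation between pain and acute phase proteins in order to", followed by two bullets of equal rank, "predict the severity of pain" and "select most suitable pain relief therapy for the patient". The title calls the study observational.

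The population is described only in the title and the opening line: "Many patients undergoing laparoscopic cholecystectomy are prone to developing acute and chronic post-operative pain". No eligibility criterion in the document limits the indication for surgery.

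Materials and methods lists one set of markers, all from one post-operative sample ("The day after surgery, some serum markers are determined by a blood sample"), and NRS pain at five times up to six months. It then closes the list of data: "Other data collected for the study are: gender, age and BMI".

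The SAP paragraph describes univariate tests (Mann-Whitney, chi-square or Fisher). Variables with P below 0.05 are then "entered in a backward multivariate logistic regression model, removing the variable if" P exceeds 0.10. No sample size, pain cut-off or case mix is given.

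**The concern.** There are two separate gaps.

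**Therapy selection.** To show that a marker helps choose between therapies, a study needs data on at least two therapies and an analysis of whether their effect on pain differs by marker level. Without these, a recommendation about choice of therapy would rest on no therapy data from this study, whatever the number of patients.

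**Surgical indication.** A patient operated on for an acutely inflamed gallbladder may have higher inflammatory markers, and may also report different pain, than an elective patient. If so, marker and pain would be associated even if the marker carried no information within either group. With indication unrecorded and no pre-operative marker value to stand in for it, the study could not tell whether an association partly reflects case mix, or whether the marker adds anything to what indication already tells the clinician.

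**Working it through.** **1. Therapy selection: what is needed against what is listed**

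| Needed to show which therapy suits whom | In the plan |
|---|---|
| A record of analgesic therapy | Not listed |
| At least two regimens compared | None described |
| A marker-by-therapy analysis | None; univariate tests and one backward logistic model |

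What remains is a marker-pain association. No arithmetic is needed for this part.

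**2. Indication: how large could the effect be?**

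The plan has no figure to reproduce. From the SAP paragraph come the Mann-Whitney and chi-square or Fisher screen at P<0.05, removal at P>0.10, and final significance at P<0.05. Everything else is assumed: n = 60, 100 or 150; a proportion p of acute cases; pain group = top 30% or 50% of scores; and no true marker effect.

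Model: A is 1 for acute and 0 for elective; marker = dm·A + N(0,1); pain = dp·A + N(0,1). The correlation that indication alone induces is

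r = p(1−p)·dm·dp / √[(1 + p(1−p)dm²)(1 + p(1−p)dp²)]

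- Negligible (p = 0.05, dm = dp = 0.25): 0.0475 × 0.0625 / 1.003 = 0.003
- Middle (p = 0.3, dm = 1, dp = 0.5): 0.105 / √(1.21 × 1.0525) = 0.09
- Material (p = 0.3, dm = 1.5, dp = 0.8): 0.252 / √(1.4725 × 1.1344) = 0.19

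The planned analysis was simulated with thousands of studies per setting. Ranges run over n and the pain cut-off, and repeat runs agree within simulation error.

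| Case | Odds ratio per marker SD | Falsely significant, indication unrecorded | Falsely significant, indication recorded and screened |
|---|---|---|---|
| Negligible | 1.00-1.01 | about 4% | about 3-4% |
| Middle | 1.16-1.18 | 6-13% | 4-5% |
| Material | 1.38-1.44 | 19-49% | 4-7% |

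Both percentage columns require the marker to pass the screen and the final model. Without the screen, and with indication always kept in the model, the rate is about 4-5% throughout. Recording the field does nearly all the work.

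**3. What including indication could cost**

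The unfavourable situation is that indication raises the marker but does not affect pain. Assume n = 100, 30% acute and pain = 0.3145·marker + N(0,1), which gives a within-indication correlation of 0.3145/√(1 + 0.3145²) = 0.30. Power for pain group = top 30% / top 50%:

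| Marker shift | Screen plus model, no indication | Screen plus model, indication screened | Indication always kept in |
|---|---|---|---|
| 1 SD | 67.4 / 72.1% | 64.3 / 70.0% | 61.7 / 66.2% |
| 1.5 SD | 75.3 / 79.5% | 70.3 / 75.3% | 60.3 / 67.3% |

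- Loss when screened: 3.1 / 2.1 and 5.0 / 4.2 points, so about 2-5.
- Loss when always kept in: 5.7 / 5.9 and 15.0 / 12.2 points. Across repeat runs the range is about 4-15.

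The last column does not require the marker to pass the Mann-Whitney screen; requiring that could only lower it.

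**4. Analgesic use**

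Assume a true marker-pain correlation of 0.30, and analgesic use that lowers the NRS.

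- If use follows pain (correlation 0.6 or 0.9, use scaled to unit variance), adjusting for use gives (0.30 − 0.6 × 0.18)/√[(1 − 0.18²)(1 − 0.6²)] = 0.244, and by the same formula 0.136. Unadjusted values are 0.216 to 0.298, depending on the strength of the analgesic effect.
- If use is independent of pain, adjustment restores 0.30, against 0.294, 0.279 and 0.246 unadjusted.

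The documents do not say which situation applies.

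**The case against.** **Therapy selection is only a downstream purpose.** The stated aim is to show a correlation, and the SAP has no therapy endpoint or test. This is a fair reading, and it makes the remedy a change of wording, not of design. It does not supply data: selection stands level with prediction, and nothing marks it as a later step. A reader might infer the stronger claim that the study can contribute nothing to treatment choice. The documents do not support that, because a valid prognosis could inform later work where therapy effects are known from elsewhere.

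**The confounder is not in the documents.** True. No text mentions acute disease, case mix or an effect of indication on markers or pain, and the negligible case shows no effect. A reader might take the material case as evidence that the association is confounded. It is not evidence of that: every input is assumed. Indication could also act on pain through inflammation; adjustment then removes no bias and costs power, as in step 3.

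**Prediction does not need confounder control.** This also stands: predicting NRS under usual care is a legitimate target, and an omitted common cause does not invalidate it. But whether the marker adds to indication is itself a prediction question, and so is transfer to a centre with a different case mix. For that reason the comparison with and without indication should be routine, not reserved for causal readings.

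**Including indication costs power.** It can, but less than one might infer. Comparing the screened analysis with a plain logistic test that skips the planned screen suggests a loss of about 6-9 points. Compared like for like, the loss is about 2-5.

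**Analgesic use should be adjusted for, or never adjusted for.** Neither rule follows. Step 4 shows that the answer turns on why patients received analgesics, which the documents do not state.

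**Conclusion.** The concern holds in two parts of unequal certainty.

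The first rests on the document alone. With no therapy variable, comparison or interaction analysis, conclusions about which therapy suits whom would have no support from this study at any sample size. Association with, and prediction of, NRS under usual care remain open to it.

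The second is conditional. It is certain that indication is unlisted and unrestricted and that no pre-operative marker value is listed. That indication matters is clinical judgement, and its size here is unknown, from nothing to a several-fold excess of false-positive findings under the assumed inputs. What can be said firmly is that the study, as planned, could not find out.

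**What to change.** 1. Restate the therapy-selection clause in the Background as a hypothesis for later study, and limit conclusions to association with, and prediction of, NRS.
2. Extract surgical indication (acute or elective) from the chart, offer it to the planned screen and logistic model as a candidate covariate, and report the marker association with and without it as a routine sensitivity analysis. Keeping it in the model regardless of the screen is optional, since it adds little protection and can cost more power.
3. Optional: describe analgesics received before the day-1 NRS by pain group. Because use may follow from pain, interpret any adjustment for it with caution.

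The cost is a narrower claim, one chart field (two with the optional item), at most one more model parameter, and the possible power loss in step 3. No extra patients, visits or procedures are needed.

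### Corticosteroid given before the day-1 blood sample is neither recorded nor stated to be standardised or excluded, so if its use varies, early marker–pain associations (chiefly leukocytes and NLR) may be confounded beyond adjustment.

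*Combined protocol and SAP*

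**What the plan says.** All of the following is in the single unnumbered protocol text (Background, Materials and methods, SAP).

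- **Exposure.** "The day after surgery, some serum markers are determined by a blood sample". Leukocytes, CRP and "Neutrophil-to-Lymphocyte Ratio (NLR)" are three of the five markers; D-dimer and fibrinogen are the others. No pre-operative sample is listed.
- **Outcome.** "Pain level is assessed using the NRS scale at different times": days 1 and 7, then one, three and six months.
- **Other variables.** "Other data collected for the study are: gender, age and BMI".
- **Population.** The Background describes it only in general terms: "Many patients undergoing laparoscopic cholecystectomy are prone to developing acute and chronic post-operative pain". The text contains no eligibility criteria.
- **Adjustment.** Variables significant "at univariate analysis were entered in a backward multivariate logistic regression model, removing the variable if" P exceeds 0.10. The significance level is 0.05.

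No corticosteroid or other drug is mentioned as a data item, a standardised treatment or an exclusion.

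**The concern.** The markers are sampled after surgery and anaesthesia. A systemic corticosteroid given beforehand, whether in theatre or as long-term treatment, could act on the day-1 markers and on early pain. It would then be a common cause of exposure and outcome. Neither the markers themselves nor gender, age and BMI can stand in for it, and without a baseline sample the analyst cannot turn to a change in marker either.

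The study wants to predict how severe pain will be and to guide the choice of pain relief. If part of a marker's association with pain reflects who received a steroid, the association may be masked, exaggerated or specific to local practice. The SAP's entry rule adds to the risk: a marker weakened by confounding may fail the univariate screen and never reach the multivariable model. If exposure is not recorded, no later analysis can recover it.

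**Working it through.** **The plan's own figure.** There is none. The documents state no sample size, effect size, SD or treated share. What follows shows how large the problem could be; it does not estimate this study's bias.

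**Step 1: what the model can adjust for.** The variables available are the five markers, gender, age and BMI. Corticosteroid exposure is not one of them.

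**Step 2: formula.** Let a share p of patients be exposed. Exposure shifts the marker by a and pain by c, both in within-group SD units, and r0 is the within-group marker–pain correlation. With v = p(1 − p), the correlation seen when exposure is ignored is

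r = (r0 + a·c·v) / √[(1 + a²v)(1 + c²v)].

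**Step 3: inputs, all assumed.** NLR a = +1; CRP a = −0.5; pain c = −0.3 or −0.5; p from 0.1 to 0.9; r0 = 0 or 0.30.

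**Step 4: one case in full.** NLR, p = 0.5, c = −0.5, so v = 0.25 and a·c·v = −0.125. The denominator is √(1.25 × 1.0625) = 1.1524. A true 0.30 gives 0.175 / 1.1524 = 0.152. A true zero gives −0.125 / 1.1524 = −0.108.

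**Step 5: the range.**

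| Marker (a) | p | c | r0 = 0.30 seen as | r0 = 0 seen as |
|---|---|---|---|---|
| NLR (+1) | 0.5 | −0.5 | 0.152 | −0.108 |
| NLR (+1) | 0.5 | −0.3 | 0.199 | −0.066 |
| NLR (+1) | 0.3 or 0.7 | −0.5 | 0.173 | −0.093 |
| NLR (+1) | 0.3 or 0.7 | −0.3 | 0.213 | −0.057 |
| NLR (+1) | 0.1 or 0.9 | −0.5 | 0.242 | −0.043 |
| NLR (+1) | 0.1 or 0.9 | −0.3 | 0.260 | −0.026 |
| CRP (−0.5) | 0.5 | −0.5 | 0.341 | +0.059 |
| CRP (−0.5) | 0.5 | −0.3 | 0.324 | +0.036 |
| Either | 0 or 1 | any | 0.300 | 0 |

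Two sensitivities matter. With weaker assumed effects (NLR +0.3 SD, pain −0.2 SD), a true zero moves by only −0.015 even at p = 0.5. Conversely, the small CRP effect depends on the half-SD shift: at −1 SD, with p = 0.5 and c = −0.5, a true zero would appear as +0.108.

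**Step 6: consequence for the screen.** By the Fisher z approximation, two-sided at 0.05, the chance of significance is roughly the normal tail beyond 1.96 − atanh(r)·√(n − 3). A fall from 0.30 to 0.152 lowers it from 0.86 to 0.33 at an assumed n = 100, and from 0.99 to 0.57 at n = 200. Conversely, an induced |r| of 0.10 with no true link reaches P<0.05 with probability about 0.17 at n = 100 and 0.29 at n = 200. The planned screen for continuous variables is Mann-Whitney, so these figures are indicative only.

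**The case against.** The strongest reply is that the protocol is silent, and silence is not a rule. A reader might infer that patients are enrolled whatever drugs they take. The text does not say so: it has no eligibility criteria of any kind, so all that can be said is that no drug-related exclusion is stated. This stands.

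A reader might also infer that corticosteroid does confound the results, and in opposite directions for NLR and CRP. The documents do not support that either. Confounding needs use to differ between patients, and they do not say whether none, some or all receive it. The signs in the table follow from the signs assumed, and if the drug is given to patients expected to do worse, the net direction could change. This also stands, so the claim has to be conditional.

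Three further limits hold. Nothing shows that a shift in early pain would persist, so the argument bears mainly on day 1 and not on the scores at one to six months. No calculation covers D-dimer or fibrinogen, so a distorted ranking of all five markers is not shown. No calculation supports excluding long-term users.

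Finally, for pure prediction an unmeasured common cause does not by itself invalidate an observed association. That is correct where steroid practice stays the same. The association may still fail to carry over to patients treated differently, and the stated aim extends to choosing therapy. This reply therefore weakens the point without removing it.

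**Conclusion.** The point holds in conditional form. As written, the plan cannot adjust for systemic corticosteroid given before the day-1 sample, nor does it let a reader see whether adjustment was needed. If use varies and the drug acts on both markers and early pain, the early associations may be confounded, chiefly for leukocytes and NLR.

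Under the main assumptions (30% to 70% treated, NLR +1 SD, pain −0.3 to −0.5 SD), a true 0.30 would be seen as about 0.15 to 0.21 and a true zero as −0.06 to −0.11. The CRP effect is small for a half-SD shift. At 10% or 90% treated, a true zero moves by at most about 0.04 for NLR, and uniform use gives no bias. Treated share, effect sizes and signs are all assumptions; leukocytes are included by analogy with NLR and were not calculated separately. This is an inexpensive improvement worth making, not a demonstrated failure of the study.

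**What to change.** 1. Add to the listed data: *systemic corticosteroid before the day-1 blood sample (yes/no, including long-term use)*.
2. Report how many patients were exposed. If all or none were, say so; nothing further is needed.
3. If use varies, keep the item as a forced covariate in the leukocyte, NLR and CRP models for early pain. It should be exempt from both the P<0.05 entry screen and removal at P above 0.10. Fit these three adjusted models even when the marker fails the unadjusted screen, because the covariate cannot otherwise reveal a masked association.
4. Report a sensitivity analysis restricted to unexposed patients.

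The cost is one extra data item and one degree of freedom per model. The restricted analysis will be less precise, by an amount that cannot be stated because no sample size is given, and it tells little if nearly everyone was exposed. A yes/no item also leaves differences in dose and timing unadjusted. No change to care and no new exclusion is needed.

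### With no pain score before surgery, the study cannot separate new post-operative pain from existing pain, or test whether a marker adds to a simple pre-operative pain question

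*Combined protocol and SAP*

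**What the plan says.** The Background opens with "Many patients undergoing laparoscopic cholecystectomy are prone to developing acute and chronic post-operative pain". The aim is introduced by "The aim of the study is to show a possible correlation between pain and acute phase proteins in order to", followed by two purposes: predicting how severe pain will be, and choosing pain relief.

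Materials and methods gives one sampling time for the markers: "The day after surgery, some serum markers are determined by a blood sample". For the outcome it says "Pain level is assessed using the NRS scale at different times". The list runs from "1st post-operative day" through day 7, one month and three months to "Six months after surgery". The covariates close the list of data: "Other data collected for the study are: gender, age and BMI".

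The SAP paragraph describes univariate tests (Mann-Whitney, chi-square or Fisher's exact), then a backward logistic regression on variables with P<0.05, with removal above P=0.10. It describes no baseline adjustment and no change from baseline.

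**The concern.** The Background speaks of patients "prone to developing acute and chronic post-operative pain". To say that pain developed after surgery, one has to know what was there before it. People who come to cholecystectomy may already have pain from gallbladder disease, and some may also have inflammation. If so, a high day-1 marker and a high score at 1, 3 or 6 months could both go back to the state in which the patient arrived.

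Two conclusions that readers will want from this study are then out of reach. The first is that a marker predicts new or chronic post-operative pain, as distinct from pain that was present and persisted. The second is that a blood test tells the clinician more than a pre-operative pain question would. The second bears directly on the stated purposes, because a marker helps in choosing pain relief only to the extent that it adds to what is easily known already.

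**Working it through.** **Step 1: is baseline pain available in any form?** The schedule and covariate list in Materials and methods give:

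| Item | Timing |
|---|---|
| NRS | day 1, day 7, 1, 3 and 6 months, all after surgery |
| Markers | once, the day after surgery |
| Other data | gender, age, BMI |

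No pre-operative score, pain history or indication for surgery is listed. The day-1 NRS cannot stand in for one: it is taken after surgery, on the same day as the markers, and is itself one of the outcomes.

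**Step 2: can the SAP repair this?** No. The logistic model can hold only variables that were collected.

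**Step 3: how large could the effect be?** The documents give no sample size, effect size or correlation, so there is no planned figure to reproduce and every input below is an assumption. Let *a* be the correlation of pre-operative pain with the marker, *b* its correlation with later NRS, and *p* the marker-pain correlation once pre-operative pain is held fixed. Then

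crude r = p × √[(1−a²)(1−b²)] + a × b.

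With no marker effect (p = 0) this reduces to a × b:

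- 0.1 × 0.3 = 0.03
- 0.3 × 0.3 = 0.09
- 0.3 × 0.5 = 0.15

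**Step 4: how often would that reach P<0.05?** By Fisher z, two-sided (the SAP does not state sidedness), let δ = atanh(r) × √(n−3). The probability is Φ(δ−1.96) + Φ(−δ−1.96). For r = 0.15 and n = 200, δ = 0.1511 × √197 = 2.12, which gives 0.564.

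| Induced r | n=50 | n=100 | n=200 |
|---|---|---|---|
| 0.03 | 5.5% | 6.0% | 7.1% |
| 0.09 | 9.5% | 14.4% | 24.5% |
| 0.15 | 17.9% | 31.9% | 56.4% |

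Fisher z is not a planned test. With Mann-Whitney, which is planned, comparing the marker between higher-pain and lower-pain patients at n=200, simulation gives about 6-37% in place of 7-56%. This assumes a roughly even split of pain; a less even split lowers the upper end.

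**Step 5: direction.** For a true p of 0.30 and the same positive inputs, the crude r is 0.315 (a=0.1, b=0.3), 0.309 (0.1, 0.5), 0.363 (0.3, 0.3) and 0.398 (0.3, 0.5). The association is inflated in all four cases. With a = 0 and b = 0.5 it is 0.26. It falls to 0.10 only if the marker is negatively related to pre-operative pain (a=−0.3, b=0.5).

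**The case against.** The strongest reply is that the aim is prediction. A marker that tracks later pain predicts it whatever the cause, and the protocol makes no explicit causal or new-onset claim; the word suggesting onset appears once, in a background sentence. This stands in part. A crude association with total pain remains interpretable, and a reader who infers that the correlation would be worthless goes too far. What the reply does not answer is whether the marker adds to pre-operative pain, or whether the pain it predicts is new.

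Three other stronger readings are tempting and are not supported:

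- **That the omission could equally hide a real association.** Under the mechanism that makes the concern plausible, with pain and inflammation rising together, the bias inflates. Material hiding needs a negative link between pre-operative pain and the marker, and nothing in the documents suggests one.
- **That a large gain in precision is being lost.** If pre-operative pain explains 9-25% of outcome variance, the equivalent sample increase is 1/(1−0.09) = 1.10 to 1/(1−0.25) = 1.33, that is 10-33%. This holds for a linear model of NRS and does not carry over directly to the planned logistic model.
- **That pre-operative pain is an established common cause.** The documents give no data on its link with the markers or with later pain, and do not describe the case mix.

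It is also fair to say that the upper percentages depend on an assumed n of 200, and that at the weakest inputs the error rate is close to nominal.

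**Conclusion.** The point holds as a gap in what the study can conclude, and one that is cheap to close. On the text, pre-operative pain is not recorded and cannot be adjusted for. It follows, with no numerical assumption, that neither new-onset pain nor a marker's value beyond baseline pain can be assessed.

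That the crude association is created or inflated is conditional: it requires pre-operative pain to be related to both the day-1 marker and later NRS. Under the assumed correlations, the chance of a significant result with no marker effect ranges from near the nominal 5% to 18% (n=50), 32% (n=100) or 56% (n=200) by Fisher z, and to about 37% by Mann-Whitney at n=200. These figures show the mechanism and its range. They do not estimate what will happen in this study. If pre-operative pain is unrelated to the marker, no false association arises from this source.

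**What to change.** Add one pre-operative NRS score to the listed times, asked with the same question as the later ones. Keep it in the adjusted marker-pain models as a forced covariate, exempt from both the P<0.05 screen and backward removal. Report the marker-pain association at 1, 3 and 6 months with and without it.

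The SAP paragraph is partly in the past tense, so some or all patients may already have been operated on. A model that requires the score would drop those who lack it. For them, give the unadjusted analysis in all patients and the adjusted analysis in those with the score, or use a missing-data method stated in advance. If no baseline score can be obtained, state the limitation and confine the conclusions to total pain after surgery.

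The cost is one extra question and one case-report field, plus missing values for patients already operated on. A single score records pain only at the moment it is asked, so it reduces the problem and may not remove it.

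### At three and six months the plan records a pain level but not whether the pain comes from the operation, so unrelated pain can bias the marker associations in either direction

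*Combined protocol and SAP*

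**What the plan says.** The background paragraph states the problem as follows: "Many patients undergoing laparoscopic cholecystectomy are prone to developing acute and chronic post-operative pain". The purpose is given as "The aim of the study is to show a possible correlation between pain and acute phase proteins in order to" predict severity and choose pain relief.

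Under Materials and methods, the markers come from one sample: "The day after surgery, some serum markers are determined by a blood sample". For the outcome, "Pain level is assessed using the NRS scale at different times": post-operative days 1 and 7, then "One month after surgery", "Three months after surgery" and "Six months after surgery". The remaining data are listed in a sentence that reads as complete: "Other data collected for the study are: gender, age and BMI".

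No item is listed for the site, onset or cause of pain. The SAP paragraph has no step that separates pain due to the operation from other pain. It also gives no definition of chronic post-operative pain and no NRS cut-off for the logistic model.

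**The concern.** An NRS score measures intensity. It does not say where the pain is or why it is there. If the plan is followed as written, a six-month score of 4 at a port site and a score of 4 from a new back problem are the same observation.

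The contacts at three and six months are the ones that can speak to the chronic part of the question. They are also the ones at which unrelated pain has had most time to arise, while pain from the operation may have settled. That last step is an assumption; the plan gives no data on the course of pain.

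At stake is whether a late association, or its absence, says anything about pain from the operation. A marker that is truly related to chronic post-operative pain could look weak. The SAP adds to this, because only variables with P<0.05 at univariate analysis enter the logistic model, so a weakened marker may never be modelled. Conversely, a marker could appear predictive because it goes with some other painful condition.

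**Working it through.** The plan states no pain rate, effect size, sample size or power, so there is no figure to reproduce. The calculation below shows only the direction and plausible size of the bias. Every rate in it is an assumption.

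**Inputs (assumed).** Operation-related pain at a late contact has risk p0 in marker-low and p1 in marker-high patients. Unrelated pain has risk u and occurs independently of operation-related pain. Any pain counts as a case.

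**Formulas.**
- p1 follows from p0 and the true odds ratio (OR): odds1 = OR × p0/(1−p0), and p1 = odds1/(1+odds1).
- Observed risk: q = 1 − (1−p)(1−u) = p + (1−p)u.
- Observed OR = [q1/(1−q1)] / [q0/(1−q0)].
- With the same u in both groups, q1 − q0 = (1−u)(p1−p0), so the risk difference shrinks by the factor 1−u and the OR moves toward 1.

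**Main case: p0 = 10%, true OR 3.** The odds are 3 × 0.10/0.90 = 0.333, so p1 = 0.25. The last column is the number per group for 80% power (two-sided 5%, equal groups, no continuity correction).

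| u | q0 | q1 | Observed OR | n per group |
|---|---|---|---|---|
| 0 | 0.100 | 0.250 | 3.00 | 100 |
| 5% | 0.145 | 0.2875 | 2.38 | 130 |
| 10% | 0.190 | 0.325 | 2.05 | 164 |
| 20% | 0.280 | 0.400 | 1.71 | 244 |

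For example, at u = 10%: (0.325/0.675)/(0.190/0.810) = 0.4815/0.2346 = 2.05.

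**Other inputs, u = 10% and 20%.**
- p0 = 5%, true OR 3: observed 1.69 and 1.42.
- p0 = 10%, true OR 2: observed 1.53 and 1.36.
- p0 = 5%, true OR 2: observed 1.34 and 1.21.

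**Unrelated pain that tracks the marker.** Let u be 10% in marker-low and 20% in marker-high patients.
- True pain 10% vs 20% (OR 2.25): q0 = 0.19, q1 = 1 − 0.80 × 0.80 = 0.36, observed OR 2.40.
- True pain 10% in both (OR 1.00): q0 = 0.19, q1 = 1 − 0.90 × 0.80 = 0.28, observed OR 1.66.

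So the direction depends on whether u is the same across marker levels, and the plan collects nothing that would show this.

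**The case against.** The document is a very short summary and does not give the wording of the NRS question. Its title and background both speak of post-operative pain, so staff may ask about pain from the operation. This stands in part: the documents show that attribution is neither specified nor recorded, not that unrelated pain will in fact be scored. But post-operative can mean only that the pain came after surgery, and nothing listed secures the narrower meaning.

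The rates are chosen, not sourced. With u = 2% in the main case the observed OR is still 2.69, and a cut-off at moderate or worse pain would make u smaller. This stands, and is why the size is offered only as a range.

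A reader might infer three stronger things that the documents do not support:
- That every marker effect is diluted. This needs unrelated pain to be independent of the marker; otherwise the association can be exaggerated or created.
- That the reported frequency of chronic post-operative pain is inflated. The plan defines no chronic-pain case and does not promise such a frequency. Unrelated pain would enter by default, not by a stated rule.
- That the one-month score is equally affected. The argument from elapsed time is weaker there, and the illustration concerns late pain.

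It can also be said that the missing cut-off and primary time point come first. That is fair as a matter of order: attribution belongs in the same outcome definition. A pre-operative score would help with pain already present, but could not identify unrelated pain that starts after surgery.

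**Conclusion.** The point holds in a limited form. As written, the three- and six-month outcome cannot separate pain from the operation from other pain, although the background makes chronic post-operative pain part of the target. The resulting bias in the marker associations is toward the null if unrelated pain is independent of the markers, and possibly away from it if not.

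Under the main assumptions, a true odds ratio of 3 is seen as anything from 2.38 to 1.71, and the number needed per group rises from 100 to between 130 and 244. These figures rest on a constant u, independence of the two kinds of pain, and counting any pain as a case. The actual size cannot be derived from the documents. The calculation gives no reason to doubt the day 1 and day 7 analyses. The change should be made because it is cheap and because attribution missed at the contact can later be recovered only by recall.

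**What to change.** At the one-, three- and six-month contacts, record two items with the NRS: the site of the pain, and whether the patient attributes it to the operation (it began or changed after surgery).

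At three and six months, define the post-operative pain outcome as the NRS for pain attributed to the operation, scored 0 if there is none, and apply to it whatever cut-off the logistic model will use. Do not require an abdominal or wound site, since that would score operation-related pain felt elsewhere as 0; use site for description. Report the unrestricted NRS alongside.

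The cost is two short questions at contacts already planned and one outcome definition, with no added visit or sample. The downside is some misattribution and recall error, the more so because no pre-operative score is listed. A difference between the attributed and unrestricted analyses would show how far the conclusions depend on it.
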